6.4 Development of predictive model and new triage tools

New triage methods will be developed by combining potential predictors of outcome using multivariable logistic regression with Least Absolute Shrinkage and Selection Operator (LASSO) to avoid overfitting [14].

Two new prediction models and subsequent triage scores will be developed: one based on clinical variables measured at initial assessment only (initial assessment model) and the other based on all clinical variables (including blood tests and x-rays) measured in the emergency department (full model). Both models will be built for adult and child populations separately (subject to the number of events in each population, if not enough events are observed in the child population we will not attempt to build prediction models).

Univariable screening of predictors will not be used as a basis for inclusion or exclusion into the predictive model as what matters is the association of predictors with outcome *after* adjustment for other predictors [15]. Using the LASSO begins with a full model of all potentially relevant predictors and simultaneously preforms predictor selection and penalisation during model development to avoid overfitting. This penalisation method essentially shrinks the estimated association between predictor and outcome towards the null, in order to reduce the variability of predictions when the model is used in new datasets.

The potential predictors considered for the predictive model will be those listed in section 6.3; whether the predictor will be considered for the initial assessment model or the full model is given in each table. The sample size calculation specified that at least 20 potential prediction factors could be assessed in a multivariable model but as many as 30 or more could be considered depending on the number of cases and adverse outcome events. Before estimating the relationship between predictors and outcome in a prognostic model, the potential to collapse correlated predictors, or keep one of a set of correlated predictors will be investigated (see section 6.4.1). All continuous predictors will be included as continuous in prediction models in the first instance but the use of cut-offs will be investigated. The potential cut-points to base categorisation of continuous predictors are listed in section 6.3. Non linear prognostic effects for continuous predictors will also be investigated (see section 7.2). Any predictor with more than 50% missing data will not be considered for inclusion in the predictive model. The initial assessment prognostic model will be built first, all prognostic factors that remain in that model after model building will be included with the bloods and tests to be considered for inclusion for the full model.

The stability of derived models will be assessed using bootstrap methods with visual calibration methods (section 7.3) [16] [17].

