A sample with N=150 adverse outcome would estimate the sensitivity of a dichotomised rule, variable or test with a standard error as outlined in the table below, depending on the sensitivity at the threshold used. Estimates of specificity would obviously be very precise given the anticipated low prevalence of adverse outcome.

Sensitivity	Lower limit of 95% Cl
1.00	0.98
0.95	0.90
0.90	0.84
0.85	0.78
0.80	0.73

The same cohort could be used to identify independent predictors of outcome and develop new triage methods (objectives 3 and 4). The number of variables that could be tested as independent predictors of outcome in a multivariable model and for inclusion in a triage method would depend upon the sample size. Based on the rule of thumb of needing at least 10 events for each independent regression variable in a

logistic regression, a cohort with 150 cases with adverse outcome would allow us to test up to 15 parameters [4].

These estimates assume that each triage method and predictor variable will be used and tested on the whole cohort. However, we plan to explore whether different patients require different triage methods, particularly whether a different triage method is required for children and adults. Data from the 2009 H1N1 pandemic suggest that around a quarter to a third of adverse outcomes may occur in children [5] [6]. To increase the probability that we will have at least 50 cases with adverse outcome among children we will aim to recruit a total of 200 cases with adverse outcome rather than 150.

If we assume that the prevalence of adverse outcome is the same as our 2009 cohort (1%) then we would need to collect data from 20,000 cases to identify 200 with an adverse outcome. We have therefore used this estimate in planning, although it is likely to be an overestimate of the total numbers required given the mild nature of the 2009 pandemic. A more severe pandemic would allow more precise estimates to be made with no additional costs or would allow us to reduce the total number of cases required to identify 200 with an adverse outcome.

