confusion, rash,		·	•		•
anosmia, abdominal					
pain, diarrhoea,					
vomiting)					
Previous attendance	Yes/No	✓	~	~	✓
Current use of	Presence/Absence				.(
anticoagulants		v	v	· ·	v
Medical History	Yes/No per disease				
(Heart disease, renal					
impairment, steroid					
therapy, asthma,					
diabetes, active		1		1	
malignancy,		·	·	•	•
immunosuppression,					
other chronic lung					
disease,					
hypertension)					
Paediatric questions	Yes/No per question		~	~	\checkmark
(routine vaccination,					
taking feeds,					
parental anxiety,					
premature)					
known contact with	Yes/No per lifestyle option	~	~	 	 
Covid-19 case					÷

Lifestyle (Pregnant,	Yes/No per lifestyle option				
clinically obese,		~		\checkmark	\checkmark
tobacco/vape user)					
Central capillary	Normal/Abnormal	1	✓	✓	✓
refill					
Severe respiratory	Yes/No	~	✓	✓	✓
distress					
Respiratory	Yes/No	✓	\checkmark	\checkmark	\checkmark
exhaustion					
Severe dehydration	Yes/No	✓	\checkmark	\checkmark	\checkmark
CXR	Normal/Abnormal*	~	~		~
ECG	Normal/Abnormal*	~	~		✓

* May also be treated as categorical with normal/abnormal/not done depending on frequencies

Categorical Characteristic	Levels	Adults	Children	Initial assessment model	Full model
Ethnicity*	UK/Irish/other white				
	-South Asian				
	-East Asian				
	-Other Asian				
	-Arab	\checkmark	\checkmark	\checkmark	✓
	-African				
	-Caribbean				
	-Other black				
	-Other/Mixed				
Performance	1=Unrestricted normal activity				
status*	2=Limited strenuous activity, can do				
	light 3=Limited activity, can self	~	✓	~	~
	care 4=Limited self care				
	5=Bed/chair bound, no self care				

*We will consider combining similar categories to reduce the number of predictor variables in the model (each category counts as one predictor), particularly ethnicity where some categories may have low frequencies.

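### Section 6.4 credits the sample size calculation with capacity for 20 to 30 or more predictors; at the planned 200 events the SAP's own 10-event rule supports 13-15 in adults and 5-6 in children, against about 53 candidates

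*SAP*

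**What the plan says.** Section 2 (Sample Size) sets the rule: "Based on the rule of thumb of needing at least 10 events for each independent regression variable". It applies the rule once: "a cohort with 150 cases with adverse outcome would allow us to test up to 15 parameters". It adds that its estimates assume use of the whole cohort. Because children may need a different method and "around a quarter to a third of adverse outcomes may occur in children", it raises the target: "we will aim to recruit a total of 200 cases with adverse outcome rather than 150". At the 1% prevalence of the 2009 cohort, "we would need to collect data from 20,000 cases to identify 200 with an adverse outcome".

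Section 6.4 attributes a different capacity to that calculation: "at least 20 potential prediction factors could be assessed in a multivariable model but as many as 30 or more could be considered". It makes this conditional on how many cases and events are seen. The same section says "Both models will be built for adult and child populations separately", subject to event numbers, with no child model if events are too few. It takes the candidates from the section 6.3 tables, starts LASSO from all potentially relevant predictors and rules out univariable screening. A footnote in section 6.3 says that, for ethnicity and performance status, "each category counts as one predictor".

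**The concern.** Section 6.4 reports a result that section 2 does not contain, and the larger figures do not fit the models that will be built. The increase from 150 to 200 events was made to secure events in children. Counting those events towards a capacity of 20 uses them for a pooled model that is not planned.

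The candidate list is also longer than any of the three figures (15, 20, 30). Section 2 applies its rule to variables tested as independent predictors, so the relevant count is the candidates offered to the model and not those that survive LASSO. A reader of section 6.4 would conclude that the sample supports the search over the section 6.3 list. On the SAP's own rule it does not. The selection decides which predictors go forward to the triage score, for which the project management group suggested an upper limit of 8 factors.

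**Working it through.** **Inputs.** From section 2: 10 events per variable, 150 events for 15 parameters, a target of 200 events, 1% prevalence, and a quarter to a third of events in children. From section 6.4: separate adult and child models, with candidates taken from section 6.3. From section 6.5: a split at 400 or more events, leaving at least 200 for development.

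**The plan's own figures.** 150 / 10 = 15, as stated. 200 / 0.01 = 20,000, as stated. 200 / 10 = 20, which section 2 does not state but which matches section 6.4 if all events enter one model. Thirty needs 30 × 10 = 300 events, a figure section 2 does not give.

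**Capacity of the separate models at 200 events.**
- Adults: 200 × 2/3 = 133 to 200 × 3/4 = 150 events, so 13-15 parameters.
- Children: 200 × 1/4 = 50 to 200 × 1/3 = 67 events, so 5-6 whole parameters.

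**Candidate parameters in section 6.3, adult initial assessment model.** One per continuous or binary item, levels minus one for categorical items.
- Continuous: age, symptom duration, number of medications, respiratory rate, pulse, temperature, systolic pressure, SaO2, SaO2/FiO2, and GCS/AVPU as one term = 10.
- Binary: sex 1, presenting features 11, previous attendance 1, anticoagulants 1, medical history 9, COVID-19 contact 1, lifestyle 3, capillary refill 1, respiratory distress 1, exhaustion 1, dehydration 1 = 31.
- Categorical: ethnicity 9 - 1 = 8, performance status 5 - 1 = 4, together 12.
- Total: 10 + 31 + 12 = 53.
- Adding 13 blood tests, CXR and ECG: 53 + 15 = 68 searched overall.
- Children (3 lifestyle items out, 4 paediatric items in): 54 and 69.

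**Other ways of counting (adults).** Ethnicity and performance status as one term each: 43 and 58. Every category counted, as the footnote says: 55 and 70. The section 6.3 cut-offs in place of linear terms: about 63 and 85. All exceed 30. Fractional polynomials would add terms.

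**Events per candidate before reduction (adults).**

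| Events | Capacity at 10 each | 53 candidates | 68 candidates |
|---|---|---|---|
| 133 | 13 | 2.5 | 2.0 |
| 150 | 15 | 2.8 | 2.2 |
| 200 (development half of 400) | 20 | 3.8 | 2.9 |
| 300 (development half of 600, i.e. 3% of 20,000) | 30 | 5.7 | 4.4 |

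The last two rows treat every development event as adult, which favours the plan. On the lenient count of 43, the adult initial model has 133/43 = 3.1 to 150/43 = 3.5 events per candidate. Ten events for each of 53 candidates would need 530 events in the adult development data.

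**The case against.** Several points on the other side stand.

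- A reader might infer that 15 and 20 contradict each other, or that section 2 is wrong. Neither follows. They are one rule at 150 and 200 events, and section 2 states both its event count and its whole-cohort assumption. With a quarter of 200 events in children, adults keep 150 events and 15 is right for them.
- Section 6.3 is a starting pool. The SAP plans to consider merging categories (6.3), to keep one of each highly correlated group and explore PCA (6.4.1), to drop predictors with more than 50% missing (6.4, 7.1), and to explore removing features with implausibly low recorded prevalence (Appendix 1). The ratios above therefore describe the list before reduction. None of these steps, however, says how short the list must become.
- It would be wrong to say that 68 terms enter one model. The full model takes the predictors retained from the initial model and adds the tests. All 68 are still searched, and the first stage alone has 53.
- It would also be wrong to say that the plan lacks protection against overfitting. Section 6.4 assigns that role to LASSO. Section 7.3.4 adds cross-validation, bootstrap optimism correction that repeats the model building, and a check on which predictors are selected. No calculation here shows that the selection would be unstable. These safeguards do not make the capacity sentence correct.
- A child ratio near one (50/54 = 0.9) might be read as a planned analysis, but section 6.4 drops the child models if events are too few. The defect is that too few has no number.
- Section 6.4 makes its figures depend on observed events, and a more severe pandemic would narrow or close the gap. The SAP still does not link observed events to the length of the list.

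**Conclusion.** The point holds as an error in section 6.4 and a missing link between events and candidates. The sample size calculation did not specify 20 or 30 predictors. At the planned 200 events, the SAP's own rule supports 13-15 parameters in adults and 5-6 in children. The adult initial list of about 53 is 53/15 = 3.5 to 53/13.3 = 4.0 times that capacity before reduction.

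This rests on the SAP's 10-event rule, its 200-event target, its assumed share of events in children, and a hand count with linear terms and reference coding. The conclusion survives the most lenient count (43). The size of the gap depends on how many events occur and how far the list is cut, and the SAP fixes neither.

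**What to change.** 1. Correct the section 6.4 sentence to give capacity per model and population: 13-15 parameters in adults and 5-6 in children at 200 events, and otherwise development events divided by 10.
2. State the actual candidate counts beside it (53 and 68 for adults, 54 and 69 for children), with the counting convention.
3. Choose one justification. Either tie the reduction already planned to that capacity, completing it without reference to outcome before LASSO, or drop the 10-event argument for the LASSO models and report the expected shrinkage for the full list.
4. Give the number of child events below which no child model is fitted.
5. Leave 15 parameters at 150 events in section 2, with a note that the events are those in the population being modelled.

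The cost is SAP wording and a little more analysis work, with no new data. The stated capacity becomes less favourable.

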6.4.1 Investigating correlation between prediction factors

The correlation between prediction factors will be investigated informally using scatterplots and investigatory analyses will be performed to see if the dimensions (number of predictor variables) can be reduced using

17

Principle Components Analysis (PCA), although it is possible that some correlated predictors will be dropped out of the regression model as part of the selection process performed during LASSO regression. For factors that appear highly correlated only one factor will be chosen for inclusion in the prediction model. The availability of data for each factor will be an important consideration in the decision to take forward one of a correlated group of factors, as this represents which factor is more often routinely collected, and also reduces uncertainty in model building.

6.4.1 Converting the predictive model into a triage tool

Integer weights will be assigned to each category of predictor variable according to the coefficient derived from a multivariable model using categorised continuous predictors. This will generate a composite clinical score in which risk of adverse outcome increases with the total score.

Clinical members of the PMG will review the multivariable prediction models and provide input into the derivation of the triage tools. They will input into the following:

- Reviewing the multivariable prediction model for
 - o Clinical credibility of predictors included in the model
 - o Clinical credibility of the direction and magnitude of effect of predictors in the model
- Deciding whether coefficients can be rounded to integer values
- Deciding if using cut-offs for continuous variables are appropriate and choosing the number and placement of cut-offs (it is expected existing cut-offs will be used as specified in section 6.3 as 'optimal' cut offs found in the models may not translate to other cohorts)
- Reviewing the number of predictors included in the prediction model and deciding if these need to be reduced for ease of use in the emergency department setting (initial discussion in the PMG suggested 8 factors as an upper limit).

A threshold for decision making will be decided upon based on clinical review but will include the following

• A cut-off that ensures sensitivity exceeds 95%

6.5 External validation of prediction models and new triage tools

The population will be split into a development and validation cohort if at least 400 adverse outcomes are recorded (resulting in at least 200 events in each cohort). This will provide sufficient power for the triage tools to be validated [18]. We anticipate there will be insufficient events to split the child cohort and hence this population will not be split. The cohort will be split by date across certain sites. A table of characteristics for the development and validation cohort will be presented to show how the cohorts differ.

The final logistic regression models (both the initial assessment model and full model) will be externally validated by applying the predictive model and triage tools and assessing calibration, discrimination and net benefit in order to assess reproducibility. The validation cohort will also be used to compare the newly developed triage tools against the existing triage tool that performed the best in the development cohort (based on AUROC) by comparing AUROC for these tools.

In order to assess transportability of the new triage tools into different populations or settings, future cohorts must be used to examine heterogeneity in performance across different populations and settings.

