6.2 Existing triage tools

We will evaluate the following existing triage methods:

- CURB-65 [7]
- PMEWS [8]
- The Swine Flu Hospital Pathway [9]
- NEWS2 [10]

- The WHO decision-making algorithm for hospitalisation with pneumonia [11]
- POPS [12]
- COAST [13]

The triage tools will be retrospectively applied to the data by the study statisticians. CURB-65 and PMEWS will be evaluated in adults only, NEWS2 will be evaluated in adults excluding pregnant women, POPS will be evaluated in children only. Details of scoring and handling missing data for the triage tools are given in sections 8.2 to 8.5. Existing triage tools will be assessed by plotting the ROC curve and calculating the area under the ROC curve (c-statistic) for discriminating between cases with and without adverse outcome. Sensitivity, specificity, positive predictive value and negative predictive value at key decision making thresholds will be calculated and presented:

Tool	Threshold
CURB-65	0-1 versus 2-5
PMEWS	0-2 versus 3+
The Swine Flu Hospital Pathway	0 versus 1+
NEWS2	0-4 versus 5-20, 0-4 versus 50-20 or scoring at least
	3 in one category
WHO	0 versus 1
POPS	0-4 versus 5+
COAST	0-2 versus 3+

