8.2 CURB-65

The CURB-65 score uses five parameters, each scoring 1 point when positive and zero if negative, to give a total score between zero and five.

Five parameters:

- 1. Confusion: GCS-V is less than 4 or GCS total is less than 15 or AVPU is recorded as V, P or U
- 2. Urea: Raised blood urea nitrogen over 7mmol/litre
- 3. Respiratory: rate of 30 breaths per minute or more
- 4. Blood pressure: diastolic BP is 60mmHg or less or systolic BP is 90 mmHg or less
- 5. Age: 65 years or more

Missing data: The rules above effectively classify missing data as normal. Low rates of missing data are expected for all parameters except urea. The CRB-65 score [7] is recommended for community settings where access to blood testing is more limited. It is the same as CURB-65 but is a 4-point scale that does not include urea with the threshold remaining as <2 for low risk, 2+ for high risk. Therefore an alternative way of handling missing data for urea is to calculate the CRB-65 score. Further sensitivity analysis may be considered if physiological variables have missing rates > 5%. If a patient has fewer than three of the five parameters complete, the score will not be calculated.

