8.3 PMEWS

PMEWS uses six physiological parameters and patient parameters to calculate a score from zero to 19. The score is calculated by taking the score in the table below dependent on each of the six physiological parameters then adding points for two patient parameters after if they are positive.

Physiological:

Score	3	2	1	0	1	2	3
Respiratory Rate	≤8			9-18	19-25	26-29	≥30
SaO ₂	<89	90-93	94-96	>96			
Pulse Rate	≤40	41-50		51-100	101-110	111-129	≥130
Systolic BP	≤70	71-90	90-100	>100			
Temperature		≤35.0	35.1-36.0	36.1-37.9	38-38.9	≥39	
Neuro				Alert	Confused Agitated*	Voice	Pain Uncon

* confused/agitated will be defined based on GCS-V<4 or GCS total<15, or if confusion is ticked as a presenting feature

Patient:

- 1. Add 1 point if age>65
- 2. Add 1 point if either:
 - a. Patient lives alone / no fixed abode or
 - b. has a co-morbidity (respiratory, cardiac, renal, immunosuppressed, diabetes)
 - c. performance status is more than two suggesting limited activity can self-care, limited activity limited self-care, or bed/chair bound no self-care.

Missing data: If data is missing one or two variables then the normal score (zero) should be assumed. If more than three variables are missing the patient should be excluded. These rules effectively classify

missing data as normal. Low rates of missing data are expected for the physiological parameters and age. The remaining parameters only account for one point and therefore would be within the range of using the patient data. Sensitivity analysis will be considered if physiological variables have missing rates > 5%. If AVPU is missing and GCS is recorded, impute the following AVPU scores using GCS: 0 if GCS=15, 1 if GCS=12-14; 2 if GCS=9-11 and 3 if GCS<9.

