8.4 Swine Flu Hospital Pathway

The Swine Flu Hospital Pathway consists of seven criteria, if any one of the criteria meet the threshold they should be admitted. The criteria thresholds are different for adults and children, these are in the table below.

Criteria	Critoria	Adult Threshold	Child Threshold
Label	Cinteria	Addit Threshold	
A	Severe respiratory distress	Severe breathlessness (severe	Lower chest wall indrawing, sternal
		respiratory distress ticked on	recession, grunting or noise breathing
		form)	when calm (severe respiratory distress
			ticked on form)
В	Respiratory rate	Over 30 breaths per minute	50+ breaths per minute if under 1, 40+
			breaths per minute if 1+ years
С	Oxygen saturation	≤92% on pulse oximetry,	≤92% on pulse oximetry, breathing air
		breathing air or on oxygen	or on oxygen
D	Respiratory exhaustion	New abnormal breathing pattern	Exhaustion or apnoeic episode (20+
		(respiratory exhaustion ticked on	second pause in breathing) (respiratory
		form)	exhaustion ticked on form)
E	Dehydration or shock ^a	Systolic BP <90 mmHg and /or	Sternal capillary refill time >2 seconds,
		diastolic BP <60 mmHg.	reduced skin turgor, sunken eyes or
		Sternal capillary refill time >2	fontanelle
		seconds, reduced skin turgor	
F	Altered conscious level ^b	New confusion, striking agitation	Strikingly agitated or irritable, seizures
		or seizures	or floppy infant
G	Other clinical concern ^c	Another clinical concern	Another clinical concern

a) dehydration or shock will be defined in adults if they are labelled as having severe dehydration, or
Systolic BP <90 mmHg and /or diastolic BP <60 mmHg, or central capillary refill is categorised as abnormal.
In children it will be defined as having severe dehydration or central capillary refill categorised as abnormal.
B) Altered conscious will be positive if GCS is less than 15 or AVPU is anything other than A. C) Other clinical concern is not recorded in the data, two scores will be calculated, one where point G is ignored and the Swine Flu hospital pathway is calculated based on the first 6 items, and another where clinical concern is considered positive if NEWS2>4 or any parameter in NEWS2 is given a score of 3.

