8.8 COAST

COAST will be scored in children only using the 2018 COAST ED charts; there is a separate chart used to score infants (0-1years), preschool (1-4 years), schoolage (5-12 years) and teenage (13-18 years) which are not included in this SAP. COAST is scored by giving one point for each of

- Doctor/nurse/family concern
- abnormal heart rate for age

- abnormal respiratory rate for age
- abnormal SaO2
- mod/severe respiratory distress
- altered consciousness
- pain score

A modified COAST score will be calculated for children, to reflect the data we are collecting

- Excluding pain score
- Only recording severe respiratory distress
- Only recording score for parental concern (parental anxiety)

Hence, the COAST score is out of a possible 6 and will only be scored if at least 3 of the factors are available. If at least three of the factors are available the missing factors will be assumed normal (score 0).

Neme	No. of	6	Description	
Name	items	Score range	Description	Interpretation of score
CURB-65	5	0 - 5		0-1 = low risk, 2 = intermediate risk, 3-5 =
				high risk
PMEWS	8	0 - 19		0 – 2 = low risk, 3+ = high risk
Swine flu	7	N/A		Any one item is positive then should be
hospital				considered a risk
pathway				
NEWS2	7	0 - 20		0 – 4 low risk, any score of 3 on one or 5+
				high risk
WHO	5	0,1		0 = do not admit, 1 = admit
POPS	7	0-14		0-4 low risk 5+ high risk
COAST	6	0-6		0-2 low risk, 3+ high risk

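### Choosing and testing the only comparator on AUROC puts the 0/1 WHO rule at a disadvantage, so the new tool may never be compared with it at the high sensitivity the plan aims for

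*SAP*

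**What the plan says.** Section 6.2 of the SAP assesses each existing tool by plotting its ROC curve and "calculating the area under the ROC curve (c-statistic) for discriminating between cases with and without adverse outcome". It adds: "Sensitivity, specificity, positive predictive value and negative predictive value at key decision making thresholds will be calculated and presented".

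Section 6.5 applies if there are enough events to split the cohort. It takes one existing tool forward and compares the new tools "against the existing triage tool that performed the best in the development cohort (based on AUROC) by comparing AUROC for these tools". The child cohort is not expected to be split, so in practice this concerns adults.

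The adult tools differ in how finely they are scored:

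- **WHO:** two levels. The triage tool summary table (8.9) reads "0 = do not admit, 1 = admit".
- **CURB-65:** five parameters "to give a total score between zero and five", so six levels.
- **PMEWS:** parameters used "to calculate a score from zero to 19", so 20 levels.
- **NEWS2:** 0 to 20, so 21 levels. Section 8.5 specifies the raw score for ROC analysis.
- **Swine Flu Hospital Pathway:** "if any one of the criteria meet the threshold they should be admitted". The summary table gives its score range as N/A and 6.2 gives the threshold as 0 versus 1+. Whether its ROC curve uses the 0/1 rule or a count of criteria is not stated.

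For the new tools, the section on converting the model into a triage tool (6.4.1) requires the thresholds to include this one: "A cut-off that ensures sensitivity exceeds 95" per cent.

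**The concern.** AUROC averages performance over all thresholds a tool offers. A 0/1 rule offers one, and the area beneath it is that of two straight lines through a single point. A multi-level score with the same underlying discrimination collects extra area, including at thresholds nobody would use for triage. Selecting the comparator on AUROC therefore handicaps the 0/1 rule for a reason unrelated to how well it works where it is used.

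The handicap grows as the rule's operating point moves towards high sensitivity, which is the region the SAP wants for the new tool. What is at stake is the content of the validation. A rule that matches or beats the multi-level tools at that operating point could be passed over, and the new tool would then be set against a comparator that is easier at the relevant threshold.

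**Working it through.** The SAP states no figure for this point, so there is nothing of its own to reproduce. It gives no sensitivity or specificity for WHO and no observed AUROC for any tool. The values below are illustrations over an assumed range of 0.60 to 0.90, which includes the planning value of 0.80 in section 2.

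**1. AUROC of a 0/1 rule.** AUROC = (sensitivity + specificity)/2. Examples:

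- 0.95 and 0.30 give 0.625
- 0.90 and 0.50 give 0.70
- 0.90 and 0.70 give 0.80
- 0.80 and 0.80 give 0.80

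**2. Loss from using a single cut.** Assume an equal-variance binormal underlying score with AUROC A, so the separation is d = √2 × Φ⁻¹(A).

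- Best single cut: sensitivity = specificity = Φ(d/2), so AUROC = Φ(d/2).
- Cut at 95% sensitivity: specificity = Φ(d − 1.645), and AUROC = (0.95 + specificity)/2.

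For A = 0.80, d = 1.190. The best cut gives Φ(0.595) = 0.724. At 95% sensitivity, specificity is Φ(−0.455) = 0.325 and AUROC is (0.95 + 0.325)/2 = 0.637.

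| Underlying AUROC | 0/1 rule, best cut (loss) | 0/1 rule at 95% sensitivity (loss) |
|---|---|---|
| 0.60 | 0.571 (0.029) | 0.525 (0.075) |
| 0.70 | 0.645 (0.055) | 0.567 (0.133) |
| 0.80 | 0.724 (0.076) | 0.637 (0.163) |
| 0.90 | 0.818 (0.082) | 0.758 (0.142) |

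**3. What a 0/1 rule needs in order to tie.** Setting Φ(d/2) equal to the multi-level AUROC gives d = 2 × Φ⁻¹(AUROC) and an underlying value of Φ(d/√2). To tie a score of 0.70 or 0.80 at its best cut, the rule needs an underlying AUROC of about 0.77 or 0.88.

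**4. A better rule that still ranks lower.** Take a rule cut at 95% sensitivity from a scale with A = 0.85. Its specificity is Φ(1.466 − 1.645) = 0.429, against 0.325 for a score with A = 0.80 at the same sensitivity. Its AUROC is (0.95 + 0.429)/2 = 0.689, against 0.80. From a scale with A = 0.90, specificity is 0.567 and AUROC 0.758, still below 0.80.

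Simulated cohorts (200 events, 19,800 non-events, correlation 0.6, 500 runs per scenario, 21-level score with AUROC about 0.80) agree. The first rule was selected in 0 of 500 runs and the second in under 1%.

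**5. Does the number of levels drive the whole ranking?** At A = 0.80, with cuts at equally spaced normal quantiles, 2, 6, 20 and 21 levels give 0.724, 0.790, 0.799 and 0.799. The largest gap among CURB-65, PMEWS and NEWS2 is 0.799 − 0.790 = 0.009. The effect matters only for a two-level rule.

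**The case against.** The strongest reply is that taking the existing tool with the highest AUROC gives the new tool its hardest opponent on the metric used. Section 2 also frames validation around AUROC (0.85 versus 0.90), so selection and comparison are consistent with it. That stands on AUROC itself. It does not carry over to a fixed high sensitivity, where step 4 shows that the tool with the higher AUROC can have the lower specificity.

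Second, 6.2 already reports threshold measures for WHO, and 6.5 already mentions net benefit. Both are true, and a careful reader could set WHO's operating point beside the new tool's. But the 6.2 measures are taken at each tool's own threshold, so at differing sensitivities. Section 6.5 uses them neither to choose the comparator nor in the comparison, and it names net benefit for the new models and tools, not for the existing tool.

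Third, the size is hypothetical. This stands. The documents do not say that WHO is a strong rule, and the 95% target belongs to the new tool's cut-off. The simulated 1% prevalence with 200 events in the development cohort also differs from the severe pandemic (above 3%) for which section 2 foresees a split.

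A reader might go further and infer that a 0/1 rule cannot win on AUROC. It can: 0.80 sensitivity with 0.80 specificity gives 0.80, and in the same simulation a rule cut optimally from a 0.90 scale was selected in 88% of runs. A reader might also infer that the ranking of existing tools merely reflects their number of levels. Step 5 rules that out for the three multi-level scores.

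**Conclusion.** The point holds in a limited form. Selecting and testing the sole comparator on AUROC disadvantages WHO by about 0.03 to 0.08 at its best cut, and by about 0.08 to 0.16 at 95% sensitivity, over underlying AUROCs of 0.60 to 0.90. These sizes rest on the equal-variance binormal assumption. That a 0/1 rule has only (sensitivity + specificity)/2 to compete with is simple arithmetic.

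The scope is the adult cohort, if it is split, and one tool: WHO. The Swine Flu Pathway joins it only if its ROC analysis uses the 0/1 rule, which the SAP leaves open.

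The consequence is a possible gap in the comparison, not a demonstrated bias in favour of the new tool. It would be too strong to conclude that the existing-tool results under objective 1 mislead: 6.2 reports the measures side by side and sets no ranking rule. Nor does the SAP contain a rule declaring the new tool superior to every existing one. This is a cheap improvement worth making, not a defect that invalidates the validation.

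**What to change.** In 6.5, keep the AUROC comparison of the new tools with the best multi-level existing tool. Add, in the adult validation cohort, a paired comparison of each new score with WHO, and with the Swine Flu Pathway if it is analysed as 0/1:

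- In the development cohort, fix the new score's cut-off at the nearest attainable value at or above the rule's sensitivity, so that no cut-off is chosen on validation data.
- In the validation cohort, compare sensitivity and specificity (or net benefit) in the same patients, with paired confidence intervals.

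In 6.2, state the scale used for the Swine Flu ROC curve.

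The cost is a few lines of SAP text and one or two paired comparisons per new tool on data already held. The drawbacks are that more than one comparator must be reported, each separately, and that integer scores may match a rule's sensitivity only approximately. For that reason both sensitivity and specificity should be shown.
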